5 SAMPLE SIZE AND POWER

The primary objective of this study is to assess the pharmacodynamic activity of immunomodulatory biomarkers following treatment with nivolumab and nivolumab in combination with ipilimumab. It is of interest to ensure precision of the estimate of the ratio of on-treatment biomarker assessments to baseline levels in Part 1 Cohorts 1 and 2. Assuming that a biomarker is measured as a continuous variable, 40 subjects per cohort will provide the following confidence that the estimate of the ratio of on-treatment to baseline values will be within 20% of the true value:

Table 5-1: Probability that estimated ratio of on-treatment to baseline value is within 20% of true value

Intra-subject Standard Deviation (log-scale)	0.2	0.3	0.4	0.5	0.6	0.7	0.8
Probability	100%	100%	97%	93%	86%	80%	74%

For example, for a biomarker with an intra-subject standard deviation of 0.5, if the true ratio of post-baseline to baseline geometric mean is 1.2 (increase from baseline is 20%), there is 93% probability that the estimated ratio would be within 0.96 and 1.44 (or a percent change between -4% and 44%). If the true increase from baseline is 60%, for a biomarker with the same variability, then there is 93% probability that the estimated percent change would be between 28% and a 92%.

More specifically, preliminary data analysis of activated and memory CD4 and CD8 T cells in CA209003 project an intra-subject standard deviation on the log-scale between 0.5 and 0.6. Assuming this variability estimate is applicable to this study, there is 86%-93% probability that the geometric mean ratio of on-treatment to baseline T cell subset levels will be within 20% of their true value.

It is of interest to ensure precision of the estimate of the proportion of subjects with increased activated T cell on-treatment (at optimal window for biopsy) in part 2 and part 3 Arms A-C. With a total of 30 subjects (from part 2 and 3) treated in Arm A (with biopsy collected at optimal on-treatment window), the maximum width of the exact 2-sided 95% confidence interval (CI) is 37% when the proportion of subjects with increased activated T cells is expected to be in the 20% to 60% range. The 95% exact CIs are presented in Table 5-2.

Table 5-2: 95% Exact CI for Proportion of Subjects with Increased Activated T cell On-treatment

Proportion	20%	30%	40%	50%	60%
95% Exact CI	(7.7%, 38.6%)	(14.7%, 49.4%)	(22.7%, 59.4%)	(31.3%, 68.7%)	(40.6%, 77.3%)

With a total of 10 subjects treated in Arm B (with biopsy collected at optimal on-treatment window), the maximum width of the exact 2-sided 95% CI is 59% when the proportion of subjects with increased activated T cells is expected to be in the 20% to 30% range. The 95% exact CIs are presented in Table 5-3.

Table 5-3: 95% Exact CI for Proportion of Subjects with Increased Activated T cell On-treatment

Proportion	20%	30%
95% Exact CI	(2.5%, 55.6%)	(6.7%, 65.3%)

For example, if the observed proportion of subjects with increased activated T cell is 20% (data from CA184-004 indicate that ~25% of metastatic melanoma subjects have an intratumoral, activated T cells with ipilimumab alone), there is 95% probability that the exact CI (2.5%, 55.6%) will cover the true proportion.

Approximately, 10 subjects will be treated in Arm D and 10 subjects in Arm E to provide additional information regarding pharmacodynamic activity of immunomodulatory biomarkers

[figure not shown]
following treatment with nivolumab and nivolumab in combination with ipilimumab. Administration of nivolumab or nivolumab in combination with ipilimumab to 10 subjects per arm provides 90% probability of observing at least one occurrence of any adverse event (or one response) that would occur with a 21% incidence in the population from which the sample is drawn.

6 STUDY PERIODS, TREATMENT REGIMENS, AND POPULATIONS FOR ANALYSES

6.1 Study Periods

Subjects will complete up to four periods of the study (Screening, Treatment, Follow-up, and Survival Follow-up). A study schematic is presented in Figure 6.1-1.

Figure 6.1-1: Study Schematic

* At the completion of two years of therapy, those subjects who are benefiting and meet criteria may continue after discussion and agreement between the Investigator and Medical Monitor and will enter the Extension Period (See Protocol Section 4.3.7).

**Subjects may be treated beyond PD, refer to Protocol² Section 4.3.8.

6.1.1 Screening Period

Subjects will go through a screening period of no longer than 28 days. Screening period begins by establishing the subject's initial eligibility and signing of the informed consent form (ICF). Subject is enrolled using the Interactive Voice Response System (IVRS).

Baseline evaluations or events will be defined as evaluations or events that occur before the date and time of the first dose of study treatment. In cases where the time (onset time of event or evaluation time and dosing time) is missing or not collected, the following definitions will apply.

- Pre-treatment AEs will be defined as AEs with an onset date prior to, but not including, the date of the first dose of study treatment.
- Baseline evaluations for vital signs (including ECOG status), pulse oximetry, and ECG will be defined as evaluations with a date on or prior to the date of first dose of study treatment, since these procedures are to be performed prior to dosing as specified in Protocol Section 5.3 and Tables 5.1B, D, and E².
- Baseline evaluations for laboratory values will also be defined as evaluations with a date on or prior to the date of first dose of study treatment, in an alignment with the core safety SAP for CA209³.

If there are multiple valid assessments at baseline, then the assessment that is closest to the date (and time, if collected) of the first dose of study treatment will be used as the baseline in the analyses. If multiple assessments are collected at the same date (and time, if collected), then the assessment with the latest database entry date (and time, if collected) will be considered as baseline.

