Procedure	Treatment Cycle = IV infusion q 2 weeks for 8 weeks				End of Treatment Visit	Notes
	Day 1	Day 15	Day 29	Day 43		
Safety Assessments						
Physical Examination	X	X	X	X	X	Done weekly in Cycle 1; to include body weight
Vital Signs (including ECOG Performance status)	X	X	X	X	X	Measured before and after study drug administration. Includes body temperature, respiratory rate, seated blood pressure and heart rate. Blood pressure and heart rate should be measured after the subject has been seated quietly for at least 5 minutes. Done weekly in Cycle 1 only.
Pulse oximetry	X	X	X	X	X	Collected at rest for at least 5 minutes, before each study drug administration. Oxygen levels will be used in combination with clinical signs and symptoms and radiographic images to evaluate pulmonary/respiratory status. Changes in O ₂ levels will not be used in isolation to document or diagnosis pulmonary toxicity.
Monitor for Adverse Events	X	X	X	X	X	All Non-Serious Adverse Events will be collected from Day1 until the subject's 100 days post discontinuation of dosing or subject's participation in the study if the last scheduled visit occurs at a later time All Serious Adverse Events must be collected from the date of the subject's written consent until 100 days post discontinuation of dosing or subject's participation in the study if the last scheduled visit occurs at a later time
Review Concomitant medications	X	X	X	X	X	
Laboratory Tests	X	X	X	X	X	To include CBC with differential, Complete Metabolic Panel (Na, K, Cl, CO ₂ , BUN, Cr, eGFR, AST, ALT, Alk Phos, Albumin, Total Bilirubin, Total Protein, Calcium, glucose), direct bilirubin, lipase, LDH, magnesium, phosphorus

Table 5.1B: CA209038 Treatment Procedural Outline, Part 1 (Cohorts 1 and 2)						
Procedure	Treatment Cycle = IV infusion q 2 weeks for 8 weeks				End of Treatment Visit	Notes
	Day 1	Day 15	Day 29	Day 43		
ECG	X				X	Single 12-lead ECGs will be collected at screening and prior to dosing on Day 1 of every other treatment cycle starting with Cycle 1. On Day 1 of Cycles 1, 2, and 4, an End of Infusion (EOI) ECG will be collected, as well. Electrocardiogram recording should be obtained just prior to as the serial PK samples as indicated in Table 5.5A.
Chest radiograph						As clinically indicated
Serum or Urine Pregnancy Test	X		X		X	Starting with Day 1 and then every other dose or every 28 days. For WOCBP within 24 hours of Study Drug Administration
Serum TSH	X					On Day 1 of each cycle
Exploratory						

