5.3 Safety Assessments

At baseline, a medical history will be obtained to capture relevant underlying conditions. Baseline signs and symptoms are those that are assessed within 2 weeks prior to treatment arm assignment. The baseline physical examination should include: weight, height, ECOG performance status, blood pressure, heart rate, electrocardiogram, O₂ saturation (pulse oximetry) and temperature; it should be performed within 28 days of treatment arm assignment. Concomitant medications will be collected from within 2 weeks prior to treatment arm assignment through the study treatment period (see [Table 5.1A](#), [Table 5.1B](#), [Table 5.1C](#), [Table 5.1D](#), and [Table 5.1E](#)).

Subjects will be considered evaluable for safety if they have received any study drug.

Toxicity assessments will be continuous during the treatment phase and follow-up phases.

Performance status and body weight should be assessed at each on study visit. Vital signs should also be taken as per institutional standard of care prior to, during and after the infusions with investigational products. Pulse oximetry should be done prior to each infusion as well. The start and stop time of the study drug infusion should be documented. If there are any new or worsening clinically significant changes since the last exam, report changes on the appropriate non-serious or serious adverse event page.

Additional measures including non-study required laboratory tests should be performed as clinically indicated.

Safety assessments will be based on the medical review of adverse event reports, results of vital sign measurements, Eastern Cooperative Oncology Group (ECOG) performance status, physical examinations, clinical laboratory results, ECGs, and imaging tests.

The incidence of observed adverse events will be categorized using the most current version of MedDRA and reviewed for potential significance and clinical importance. Adverse events will

be evaluated according to the National Cancer Institute Common Terminology Criteria for Adverse Events (NCI CTCAE) version 4.0.

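### When times are missing, the SAP's baseline rule can take a post-infusion Day 1 vital sign (or, in Part 1, ECG) as baseline, because its cited protocol sources do not place all such readings before dosing

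*SAP*

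**What the plan says.** SAP 6.1.1 starts from a sound rule: "Baseline evaluations or events will be defined as evaluations or events that occur before the date and time of the first dose of study treatment". A fallback follows for certain records: "In cases where the time (onset time of event or evaluation time and dosing time) is missing or not collected". Under it, vital signs (with ECOG status), pulse oximetry and ECG count as baseline if they are dated on or before the day of first dose. The reason given is that this is acceptable "since these procedures are to be performed prior to dosing as specified in Protocol Section 5.3" and Tables 5.1B, D and E.

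If several records qualify, the one closest to first dose is used. If they share a date (and time, where collected), "then the assessment with the latest database entry date (and time, if collected) will be considered as baseline".

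The cited protocol sources read differently for two of these procedures:

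- Section 5.3, which is not limited to any part: "Vital signs should also be taken as per institutional standard of care prior to, during and after the infusions with investigational products".
- Table 5.1B (Part 1), vital signs: "Measured before and after study drug administration".
- Table 5.1B (Part 1), ECG: a pre-dose ECG on Day 1 of every other cycle from Cycle 1, and "On Day 1 of Cycles 1, 2, and 4, an End of Infusion (EOI) ECG will be collected, as well".

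**The concern.** The fallback rests on a premise about timing that its own references contradict. Without times, the date alone cannot separate a pre-dose reading from a post-dose one. The tie-break then uses the order of database entry, which has no defined link to the order of dosing.

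Change from baseline in blood pressure and heart rate is a named secondary safety endpoint (SAP 4.2.1; Protocol 8.3.2.1) and is summarised by timepoint (SAP 7.6.10). A subject whose baseline is a post-infusion reading contributes wrong changes to that summary.

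In the same section, under the same missing-time condition, the SAP takes the cautious course for adverse events: an event counts as pre-treatment only if its onset date is before the first-dose date. For vital signs and ECG it departs from that course only because of the timing premise.

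**Working it through.** The plan gives no figure to reproduce. The check sets the premise beside its sources and then traces the selection rule.

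**Step 1. Does the pre-dose premise hold on the first-dose day?**

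| Measure | What the cited sources schedule | Premise holds? |
|---|---|---|
| Vital signs, Part 1 | Table 5.1B: before and after dosing. Section 5.3: before, during and after infusion | No |
| Vital signs, Parts 2 to 4 | Tables 5.1D and 5.1E list no post-dose reading. Section 5.3 asks for readings before, during and after infusion, following institutional practice | No, because of Section 5.3 |
| ECG, Part 1 | Table 5.1B: pre-dose and end of infusion on Cycle 1 Day 1 | No |
| ECG, Parts 2 to 4 | Tables 5.1D and 5.1E: pre-dose from Week 13, none on Day 1 | Yes |
| Pulse oximetry | Section 5.3 and Table 5.1B: before each infusion. Tables 5.1D and 5.1E: within 72 hours before dosing | Yes |

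**Step 2. Trace of the rule for a Part 1 subject with untimed Cycle 1 Day 1 records**

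1. The pre-dose and post-dose vital signs carry the first-dose date, so both qualify. The same is true of the pre-dose and end-of-infusion ECGs.
2. The closest-to-first-dose step prefers Day 1 to screening, but cannot separate the Day 1 records from each other.
3. The tie-break takes the record entered last. If that is the post-dose record, it becomes baseline.

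If both the assessment time and the dosing time are recorded, the main rule excludes the post-dose record and the problem does not arise.

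**Step 3. Effect on one subject**

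Let B be the pre-dose value, P the post-infusion value, d = P − B, and Y any later value. The correct change is Y − B. With P as baseline, the reported change is Y − P = (Y − B) − d.

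As an assumed illustration, take d = −10 mmHg. At the post-infusion reading itself Y = P, so the correct change is −10 and the reported change is 0. Every later change is reported 10 mmHg too high.

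**Step 4. Effect on an arm mean**

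If k of n subjects are affected by the same d, the mean change shifts by −(k × d)/n. The documents give neither k nor d, so the results below are a range under the assumed d = −10 mmHg:

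- n = 40 (one Part 1 cohort), k = 1: 10/40 = 0.25 mmHg.
- n = 10 (Arm B, D or E), k = 1: 10/10 = 1 mmHg; k = 2: 20/10 = 2 mmHg.
- Limits for any n: 0 if no subject is affected, 10 mmHg if all are.

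**The case against.** The strongest reply is that the governing rule is correct and the criticised text is only a fallback. Section 5.3 asks for infusion start and stop times to be documented, and nothing shows that assessment times will be missing. The SAP also restricts selection to valid assessments, and SAP 8.1 applies sponsor time-windowing standards that are not reproduced. Those might remove a record labelled post-dose. This stands as a limit on frequency. It does not repair the rationale, and the SAP itself provides for the missing-time case.

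A reader might infer more than the documents support:

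- **That the tie-break will usually pick the post-dose reading.** Nothing describes the order of data entry, and both readings could be entered together. The text supports only that it can.
- **That every subject with an untimed Day 1 reading is affected.** A lone untimed pre-dose reading is handled correctly. Error needs an untimed post-dose record that is accepted as valid and is either entered after any pre-dose record or the only Day 1 record.
- **That the review of shortened infusions is compromised.** Protocol 8.4.3 bases that review on the incidence of infusion reactions, which uses no vital-sign baseline. The explicit post-dose readings in Table 5.1B belong to Part 1, where infusions last 60 minutes. For the 30-minute infusions of Parts 3 and 4 only the Section 5.3 sentence applies, and the documents do not say that those readings enter the database.
- **That ECG conclusions are at risk.** The Day 1 ECG problem is confined to Part 1, and SAP 7.6.9 plans listings only.

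**Conclusion.** The point holds in a narrow form. The stated reason for the fallback is contradicted by the sources it cites, and where untimed pre-dose and post-dose Day 1 records coexist, a post-infusion value can be selected as baseline. For an affected subject, the first-infusion change in blood pressure or heart rate is lost and later changes are shifted by the same amount.

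The frequency is unknown. It depends on whether the case report form collects assessment times or nominal timepoints, and on the entry order, neither of which the documents show. The reach is limited to descriptive vital-sign summaries, with a minor effect on Part 1 ECG listings. Pulse oximetry is not affected, and this fallback does not touch the primary biomarker or efficacy endpoints. It is a minor correction, worth making because it is cheap.

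**What to change.** In SAP 6.1.1:

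1. Correct the rationale sentence so that it no longer says all first-dose-day vital signs and ECGs are taken before dosing.
2. For vital signs and ECG, exclude from baseline any Day 1 record whose nominal timepoint is during infusion, post-dose or end of infusion.
3. Where several untimed Day 1 records cannot be told apart, use the last assessment dated before Day 1 in place of the latest-entry tie-break.
4. Keep a lone Day 1 record as baseline if it is not labelled during infusion, post-dose or end of infusion. Table 5.1A allows the pre-treatment visit to fall on Day 1, so sending every untimed Day 1 record back to screening would discard legitimate pre-dose values.
5. Leave pulse oximetry as it is.

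The cost is a short SAP edit and a programming rule, with no change to any patient procedure. Table 5.1A schedules vital signs and an ECG at screening, so an earlier value should exist. The downside is that a few subjects would have an older baseline, from a screening period of up to 28 days. A lone post-dose record with neither time nor label would still be accepted; the documents offer no way to detect it.

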6.1.2 Treatment Period

Nivolumab will be given every 2 weeks when administered as monotherapy (Cohorts 1 and 2; Arms B and E; Arms A, C, and D after stopping ipilimumab) and every 3 weeks when administered in combination therapy with ipilimumab. Ipilimumab will be given every 3 weeks when administered as monotherapy (Arm C) or combination therapy (Arms A and D).

On days where both study drugs are given, nivolumab will be given first followed by ipilimumab and will start no sooner than 30 minutes after completion of the nivolumab infusion and after the post-nivolumab pharmacokinetic blood sample is drawn.

The treatment period is defined as starting from the date and time of the first dose of study medication. The treatment period ends 14 days after the last dose of nivolumab, if the last dose is nivolumab, and 21 days after the last dose of ipilimumab, if the last dose is ipilimumab.

6.1.3 Follow-up Period

The follow-up period begins 15 days after the last dose of nivolumab, if the last dose is nivolumab, and 22 days after the last dose of ipilimumab, if the last dose is ipilimumab.

Each patient will continue in follow-up for a maximum period of up to 100 days; follow-up office visits 1 and 2 (40-60 days and 101-120 days after the stop of study therapy).

6.1.4 Survival Follow-up Period

All patients who do not enter the Extension Period will be followed for overall survival assessment every 3 months up to 2 years from the first dose of study therapy.

6.1.5 Extension Period

At the completion of 2 years of therapy, those subjects who are benefiting and still meet study criteria may continue after discussion and agreement between the investigator and Medical Monitor and will enter the Extension Period. Patients that enter the Extension Period will be followed for overall survival assessments up to a maximum of 100 days after the last treatment dose.

